Treatment-emergent: hypoglycaemic episodes will be defined as treatment-emergent, if the onset of the episode occurs in the on-treatment period (see definition in Section 10.2).

Nocturnal hypoglycaemic episodes: episodes occurring between 00:01 and 05:59 both inclusive.

Hypoglycaemic episodes are classified according to the Novo Nordisk classification of hypoglycaemia and the ADA classification of hypoglycaemia²⁰.

Reporting of hypoglycaemic episodes:

PG should always be measured and recorded when a hypoglycaemic episode is suspected or when a hypo alarm is triggered on the iLet™.

All PG values:

≤3.9 mmol/L (70 mg/dL) or

>3.9 mmol/L (70 mg/dL) occurring in conjunction with hypoglycaemic symptoms should be reported as a hypoglycaemic episode according to the flowchart and instructions below. When a subject experiences a hypoglycaemic episode, subject should record the general information in relation to the hypoglycaemia (timing, PG measurements, symptoms etc. as described in the diary). In case a subject is not able to fill in the diary (e.g. in case of hospitalisation or at the ‘follow-up phone contact’), then investigator should report the hypoglycaemic episode in the CRF.

Upon onset of a hypoglycaemic episode the subject is recommended to measure PG every 15 minutes until the SMPG value is >3.9 mmol/L (70 mg/dL) and/or symptoms have been resolved in accordance with current guidelines²⁰.

Repeated SMPG measurements and/or symptoms, occurring within a period of 60 minutes after onset of a hypoglycaemic episode, will by default be considered as one hypoglycaemic episode until a succeeding SMPG value is >3.9 mmol/L (70 mg/dL) and/or symptoms have been resolved and should be reported on one hypoglycaemic episode form. SMPG measurements ≤3.9 mmol/L (70 mg/dL) or hypoglycaemic symptoms after the 60 minutes period shall trigger the reporting of a new hypoglycaemia episode.

In case of several low SMPG values within the 60 minutes interval, the lowest value is the one that will be reported as the SMPG value for the hypoglycaemic episode but the start time of the episode will remain as the time for the first low SMPG value and/or symptom.

The lowest value measured during the hypoglycaemic episode will be reported as the PG value for the episode. The remaining values will be kept as source data in the diary.

A hypoglycaemic episode starting without symptoms should be updated to symptomatic if the subject experiences symptoms later during the episode.

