Date:	21 January 2019
Version:	1.0
Status:	Final
Page:	1 of 4

Novo Nordisk

Protocol Amendment

no 4

**to Protocol, version 4
dated *19 Dec 2018***

Trial ID: NN1218-4360

**An Exploratory Trial investigating the Safety and Efficacy of Fast-acting Insulin Aspart in a
Closed-loop Insulin Delivery System (bionic pancreas) in Adults with Type 1 Diabetes**

**Trial phase: 2
Applicable to *all countries***

~~This confidential document is the property of Novo Nordisk. No unpublished information contained herein may be disclosed without prior written approval from Novo Nordisk. Access to this document must be restricted to relevant parties.~~

Table of Contents **"Double click to update Table of Content"**

1	Introduction including rationale for the protocol amendment.....	3
2	Changes	3

1 Introduction including rationale for the protocol amendment

In this trial the subjects will be using a blood glucose (BG) meter that has the capacity to store the date, time and values of all BG measurements taken in course of the trial. This data can be downloaded to the site computer at the site.

Following discussions at the investigator meeting, the sponsor and the investigator are in agreement that the data downloaded from the BG meter is a more accurate representation of the glucose values measured during the trial, than a collection of the data entered by the subjects in the subject diary, as the latter is a source to potential human error.

Hence, this amendment aims to modify the way of recording BG values used for CGM calibration in the subject's diary. The subject diaries will be modified to include only the date and time of the twice daily CGM calibrations performed by the subjects. This subject-entered time will be considered the approximate time, and will be used by the site staff to identify the corresponding actual time and glucose values in the downloaded BG meter data. Only the accurate dates, times, and values for CGM calibrations from the BG meter download will be entered into the CRF by the site staff. As a consequence, the subject will not be asked to correct the diary entries in case of a discrepancy with the BG meter download.

In this protocol amendment:

- Any new text is written *in italics*.
- Any text deleted from the protocol is written using ~~strike through~~.

2 Changes

Section 9.11 Self-measured plasma glucose

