Subjects will be provided with a BG meter including auxiliaries as well as instructions for use. The subjects will be instructed in how to use the device and the instruction should be repeated, if needed

The BG meters use test strips calibrated to plasma values. Therefore, all measurements performed with capillary blood are automatically calibrated to plasma equivalent glucose values, which will be shown on the display.

The BG meter provided by Novo Nordisk should be used for the measurements required in the protocol. SMPGs must be performed to calibrate the CGM sensor (section 9.10) and in the event of hypoglycaemic episode (Appendix 7) and should *for the latter* be reported in the diary, see section 9.14.

~~All SMPGs values must be recorded in the paper diary. In addition to paper diary, SMPGs performed for the calibration of the CGM sensor must also be recorded on the StudyPhone with~~

~~CGM app. The record of each SMPG value on paper diary should include date, time and value. All data from the diary must be transcribed into the CRF during or following the contact.~~

The subjects should use the SMPG values for the calibration of the CGM sensor by entering the measured values into the StudyPhone with CGM app. The record of these calibrations on paper diary should include date and time. The subjects must be instructed to bring the BG meters to the site at every site visit. The site will download the BG meter data at every site visit. Further the site will use the date and time reported by the subjects in the diary to identify the correct date, time and value in the data downloaded from the BG meter and report these in the CRF.

Documentum ObjectID : 

This is a representation of an electronic record that was signed electronically and this page is the manifestation of the electronic signature.

Document signed by:

Initials	Full Name	Date and Time of Signature (Server Time)
Meaning

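### Amendment 4 accepts the meter download as more accurate than the diary, but leaves the glucose value and reading time of reported hypoglycaemic episodes diary-entered

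*Combined protocol and SAP*

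**What the plan says.** Amendment 4, section 1, notes that the meter can "store the date, time and values of all BG measurements taken in course of the trial". It then states that "the data downloaded from the BG meter is a more accurate representation of the glucose values measured during the trial", compared with diary entries, "as the latter is a source to potential human error".

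The change itself is limited to calibrations: "this amendment aims to modify the way of recording BG values used for CGM calibration in the subject's diary", and "Only the accurate dates, times, and values for CGM calibrations from the BG meter download will be entered into the CRF". The diary keeps only an approximate calibration date and time, which site staff use to find the matching meter record.

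The amended section 9.11 begins "SMPGs must be performed to calibrate the CGM sensor (section 9.10) and in the event of hypoglycaemic episode (Appendix 7) and should" and then directs the second kind of reading, the one taken in an episode, to the diary. It adds: "The site will download the BG meter data at every site visit".

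No amendment supplied changes section 9.14, which lists hypoglycaemic episodes among the diary data transferred to the CRF. Nor does any change the Appendix 7 rules on where episode glucose comes from. The subject writes the timing and PG in the diary; "The lowest value measured during the hypoglycaemic episode will be reported as the PG value for the episode"; the other readings stay in the diary as source.

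**The concern.** The reason given for the amendment covers all glucose measured in the trial, while the remedy covers calibrations only. The self-measured values that define reported hypoglycaemic episodes still pass through handwriting, although the same readings, with date and time, are in a file the site already holds.

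At stake is avoidable misclassification in the hypoglycaemia tables: which sponsor or ADA category an episode falls in, and whether it counts as nocturnal. The point concerns the accuracy of episodes that are reported. It does not concern the search for unreported ones.

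**Working it through.** The plan gives no figure to reproduce. Section 10.1 makes no formal sample size calculation, and the documents state no diary error rate and no expected episode rate. The check is therefore mainly a tracing of the text.

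**1. Path of each reading to the CRF**

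| | Calibration reading | Reading in a reported episode |
|---|---|---|
| Stored in the meter | Yes | Yes |
| Diary entry | Approximate date and time | Timing and PG value |
| Matched to the download | Yes (amended 9.11) | Not required anywhere |
| Value and time in the CRF | From the meter | From the diary (9.14, Appendix 7) |

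**2. What the episode entries decide**

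- Sponsor classification (Appendix 7): an episode is confirmed by a PG below 56 mg/dL (3.1 mmol/L).
- ADA classification (Appendix 7): asymptomatic and documented symptomatic episodes need a PG at or below 70 mg/dL (3.9 mmol/L).
- Nocturnal label (Appendix 7): 00:01 to 05:59, both included.
- Onset (Appendix 7): the first low reading and/or symptom. The fingerstick time matters here only when a reading, not a symptom, opens the episode.

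These feed the supportive secondary count of classified episodes (sections 4.2.3 and 10.3.2.1), shown by cohort and treatment with no model specified.

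**3. What they do not decide**

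- The primary endpoint and the 2% escalation criterion use interstitial glucose from the iLet (sections 8.1.1, 9.1, 10.3.1).
- Severe hypoglycaemia is defined by need for another person's help, with no PG cut-off. PG appears only as one of several alternative supporting conditions for an assisted episode.

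**4. Illustration on assumed inputs**

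From the plan: 8 subjects per cohort, 2 periods each. Assumed: 5 reported episodes per subject-period; 2% to 10% of diary values or times wrong; 10% to 25% of those errors crossing a class boundary.

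- Episodes per cohort: 8 × 2 × 5 = 80.
- Misrecorded entries: 80 × 0.02 = 1.6 to 80 × 0.10 = 8.
- Entries that change a class: 1.6 × 0.10 = 0.16 to 8 × 0.25 = 2.

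All three assumed inputs are outside the documents. The lines show only that misrecorded entries and misclassified episodes are different counts, the second being a fraction of the first. They are not an estimate.

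**The case against.** The case on the other side has five parts.

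- **The last sentence of the amended section 9.11 might cover all self-measured readings.** It does not repeat the word calibration. But it follows a sentence about calibration records, and section 1 of the amendment restricts the CRF entries from the download to calibrations. The wider reading would also conflict with sending episode readings to the diary.
- **Errors are already reviewed.** Diaries are checked with the subject at each site visit (9.14), and monitors compare diaries and other source data with the CRF (Appendix 3, item 9). This stands in part: entries are not unreviewed, but no step requires comparing an episode with the download. The site's source document agreement (Appendix 3, item 10) is not among the documents and might say more.
- **Meter times cannot replace onset.** This stands. Symptoms may come before the fingerstick, symptomatic episodes above 70 mg/dL have no low reading, and probable symptomatic episodes have no PG at all. Taking onset from the meter would redefine it and could itself move day/night labels.
- **Calibration deserves the better source.** This stands. Section 9.10 makes calibration essential to CGM accuracy, and CGM gives the primary endpoint. A reader might infer that the sponsor put the better source on unimportant data; the documents do not support that. The CRF calibration record is not itself analysed, but it documents the calibration of the trial's main measurement.
- **The errors are likely noise.** This largely stands. Subjects are blinded to the order of settings and serve as their own controls, and nothing in the documents suggests diary error would differ between settings.

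**Conclusion.** The inconsistency is real and small. The plan keeps, for one supportive and descriptively summarised endpoint, a source that its own amendment calls less accurate, while the better record is already downloaded at every visit. The effect on episode counts cannot be estimated from the documents; only errors crossing 56 or 70 mg/dL, or the 00:01/05:59 bounds, change a class. The conclusion rests on reading the amended section 9.11 as limited to calibrations, which its context supports.

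Two stronger inferences should be resisted. First, a reader might infer that the safety decision is exposed. It is not: the escalation criteria rest on CGM time below 54 mg/dL and on severe episodes. Second, a reader might infer that a wrong diary time on the Visit 3 switch day would often assign an episode to the wrong setting, since there is no wash-out. Staff record the iLet stop and start times in the CRF (9.12), the switch takes place at a site visit, and a 2-day in-patient stay follows (Amendment 1). Such a shift is possible but would be rare.

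**What to change.** Extend the matching step in the amended section 9.11, with a corresponding line in Appendix 7:

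- For each reported hypoglycaemic episode, enter in the CRF the lowest PG and the times of the self-measured readings from the matched meter download.
- Leave the Appendix 7 onset rule unchanged (first low reading and/or symptom). Take symptom onset, symptoms and ability to self-treat from the diary.
- Use a diary PG value only when no meter record exists, and flag it in the CRF.

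The cost is a short text change and a few more readings to match per subject. Appendix 7 recommends repeat measurements every 15 minutes, so one episode may have several. The download and the matching procedure already exist, and nothing in the care of subjects changes.
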